5. METHODS

5.1 Study parameters/endpoints

5.1.1 Main study parameter/endpoint

Main parameter:

- Response to upfront therapy on PSMA-PET/CT based on PERCIST (PET Response Criteria In Solid Tumours).

PERCIST consists of a set of rules to interpretate solid tumor response on the PET/CT originally based on the FDG-PET/CT (O 2016, Fanti 2019). It looks at the tumor uptake of the PET tracer also expressed as the standardized uptake value (SUV). It divides tumor response based on the perceptual change in SUV between two (in our case) PSMA PET/CT's and the change in the amount of tumor lesions (see table 1). For the notation you also need to include the amount of time between the two PET scans. For example (35% increase, 4 weeks, five new lesions).

Table 1

Response	PSMA PET/CT interpretation
Complete response (CR)	Complete resolution of PSMA-tracer uptake in all
	lesions
Partial response (PR)	More than or equal to 30% reduction of SUV and an
	absolute drop of 0.8 SUV units
Progressive disease (PD)	More than or equal to 30% increase in SUV and
	absolute increase of 0.8 SUV units, or appearance of
	new lesions with PSMA-tracer uptake
Stable disease (SD)	Not quality for CR, PR, or PD

NB: lesions with prior radiation treatment (e.g. symptomatic bone metastasis) will not be accounted for in the PERCIST response evaluation.

Main endpoint:

- Time since start ADT to development of castration-resistant disease (CRPC). CRPC is defined by EAU guidelines (Cornford 2020) as:

Castrate serum testosterone <50 ng/dL or 1.7 nmol/L plus either:

- a. Biochemical progression: Three consecutive rises in PSA at least one week apart, resulting in two 50% increases over the nadir, and a PSA >2 ng/mL, or:
- b. Radiological progression: The appearance of new lesions: either two or more new bone lesions on skeletal scintigraphy or a soft tissue lesion on CT using RECIST (Response Evaluation Criteria in Solid Tumours) or on (PSMA-)PET/CT-imaging using PERCIST (PET Response Evaluation Criteria In Solid Tumours) (Fanti 2020, Boellaard 2015).

Symptomatic progression alone must be questioned and subject to further investigation. It is not sufficient to diagnose CRPC.

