3. STUDY DESIGN

The study is a prospective open-label, non-interventional, non-therapeutic observational cohort study. The study is performed in an outpatient setting. Total study duration will be 48 months.

Multicenter (Netherlands):

- UMC Utrecht, Utrecht (lead);
- St Antonius Hospital, Utrecht / Nieuwegein (external inclusion);
- Meander MC, Amersfoort (external inclusion);
- Amsterdam UMC, Amsterdam (external inclusion).

Patients will be treated with hormonal therapy plus upfront therapy. Indication for upfront therapy and the choice for specific combination will be made at a multidisciplinary meeting. Patients are elected for study participation after prostate cancer has been histologically confirmed and signs of multiple metastases have been confirmed on PSMA-PET/CT-imaging. The definition of multiple / high volume metastasis is: >3 metastatic lesions (any combination of either lymph node metastasis outside of pelvis, bone metastasis, or visceral metastasis). Participating centers will standard use PSMA PET/CT as first imaging choice at suspicion of metastasized disease.

Standardized imaging (Figure 1):

- PSMA-PET/CT:
 - 1. Standard of care PSMA PET/CT: At diagnosis (hormonal therapy needs to be started <4 weeks).
 - 2. Additional PSMA PET/CT: 2 months after start hormonal therapy (+/- 1 week).
 - 3. Additional PSMA PET/CT: 2 months after start of chemotherapy (+/- 1 week).

Patients continue hormonal therapy plus upfront therapy according to standard of care. Follow-up of standard of care consists of monthly outpatient checks, including standard lab tests (i.e. PSA, AF, testosterone, electrolytes, full blood count).

The results of the additional PSMA-PET/CT scans will not be blinded to patients or physicians and will not be used in clinical decision-making.

The primary endpoint is time from start of ADT to CRPC. CRPC is defined by EAU guidelines (Cornford 2020) as:

Castrate serum testosterone <50 ng/dL or 1.7 nmol/L plus either:

- a. Biochemical progression: Three consecutive rises in PSA at least one week apart resulting in two 50% increases over the nadir, and a PSA >2 ng/mL, or:
- b. Radiological progression: The appearance of new lesions: either two or more new bone lesions on skeletal scintigraphy or a soft tissue lesion on CT using RECIST (Response Evaluation Criteria in Solid Tumours) or on (PSMA-)PET/CT-imaging using PERCIST (PET Response Evaluation Criteria In Solid Tumours) (Fanti 2020, Boellaard 2015).

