4.2 Sample size calculation

Predictive modelling will be used. Besides the parameter of main interest:PSMA-PET/CT response to upfront therapy based on PERCIST (i.e. Complete response (CR), Partial response (PR), Progressive disease (PD), Stable disease (SD)) see also chapter 5.1.1 table 1, the following potential predictive factors will be taken into account (these variables have been included in subgroup analyses in earlier M+HSPC studies):

- PSA at diagnosis.
- Pathological Gleason score (ISUP Gleason grades 1-3 versus 4-5).

- Metastasis volume load (defined as 'Charteed'-study criteria; high volume defined as >5 skeletal lesions with 1 or more outside pelvis or vertebrae or visceral metastasis, low volume defined as all others).(Sweeney 2015)

- PSA response (defined as PSA nadir).
- Type of upfront therapy used.
- PSMA response to hormonal therapy as continues variable in percentage based on PERCIST (see 5.1.1).

Estimation of proportion of variation in PERCIST PSMA response was based on preliminary case series on PSMA response in M+HSPC patients.(Seitz 2018).

[figure not shown]
Sample size estimation was performed in SAS (version 9.4) PROC POWER, using a score test for a Cox proportional hazards model.

Considerations (Figure 2):

- Expected median time to CRPC: 24 months.
- Power 80%.
- Type I error (alpha) 5%, two-sided.
- Probability of event within 24 months: 0.5.
- Estimation of proportion of variation in PERCIST PSMA response (R²): 0.75 (based on linear regression of data from Seitz et al.).
- Standard deviation PERCIST PSMA response: 3.5 4 (per 10 percentage points).
- Small to medium effect (hazard ratio 1.2-1.3 per 10 percentage points PERCIST PSMA).

Assuming a standard deviation of 4, an R² of 0.75, and a hazard ratio of 1.2-1.3, the number needed to include is 150.

Around 1750 new diagnoses of M+HSPC are made in The Netherlands yearly. The collaborating centres cover ~12.5% of new diagnoses in The Netherlands (~200 cases). Assuming a study acceptance rate of 50% (low estimation), patient accrual (N=150) is expected to cover ~18 months.

[figure not shown]

Fig. 2 Considering small effect HR 1.2 - 1.3, SD 4, R-square 0.75 - 0.80 leads to sample size 130 - 150.

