7. STATISTICAL ANALYSIS

7.1 Primary study parameter(s)

The collected data will include nominal, categorical, ordinal and continuous variables.

A predictive model will be constructed. Main parameter is PERCIST PSMA response to upfront therapy. Main outcome is time since diagnosis to development of CRPC. Primary analysis will be the comparison of two Cox proportional hazards models for time to development of CRPC: the first including the six predictive factors (PSA at diagnosis, pathological Gleason score, metastasis volume load, PSA early response, type of upfront therapy, PSMA response to hormonal therapy only), mentioned in section 4.4, and the second including those six variables plus PERCIST PSMA-PET/CT response after start of upfront therapy. The models will be compared using a likelihood ratio test, and the c-statistic will be calculated to estimate the added benefit of PERCIST PSMA response above the known predictors of CRPC.

An intention-to-treat analysis will be performed (i.e. all subjects who actually receive baseline and two follow-up PSMA PET/CT scans.) will be included for analysis, even when treatment is changed early.

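### New lesions on scan 3 can make a patient both progressive on the primary predictor and a CRPC event, from the same image on the same date, and no rule or landmark prevents it

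*Combined protocol and SAP*

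**What the plan says.** **Predictor.** The primary predictor is the PERCIST response on PSMA-PET/CT from scan 2 (two months into ADT) to scan 3 (two months into upfront therapy); see sections 2, 5.1.2 and 7.1. Table 1 in section 5.1.1 gives two separate routes to progressive disease (PD). One is an SUV rise of at least 30% with an absolute rise of 0.8 units. The other is the appearance of "new lesions with PSMA-tracer uptake".

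**Endpoint.** Sections 3 and 5.1.1 define CRPC as castrate testosterone plus either a PSA limb or a radiological limb. The radiological limb (limb b) opens with "Radiological progression: The appearance of new lesions" and accepts bone scan, CT by RECIST, "or on (PSMA-)PET/CT-imaging using PERCIST (PET Response Evaluation Criteria In Solid Tumours").

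**Use of the study scans.** Section 3 states: "The results of the additional PSMA-PET/CT scans will not be blinded to patients or physicians and will not be used in clinical decision-making".

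**Analysis.** Section 7.1 compares a Cox model of six factors with the same model plus PERCIST response, by likelihood ratio test and c-statistic. The analysis set is "all subjects who actually receive baseline and two follow-up PSMA PET/CT scans". On time origin, section 7.1 says "Main outcome is time since diagnosis to development of CRPC", whereas sections 3 and 5.1.1 count from the start of ADT. Section 5.4 gives a censoring rule for loss to follow-up only. No section says how a CRPC event is dated.

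**Coding.** Section 4.2 (sample size) describes the parameter of main interest as "Complete response (CR), Partial response (PR), Progressive disease (PD), Stable disease (SD"), but sizes the study on "Small to medium effect (hazard ratio 1.2-1.3 per 10 percentage points PERCIST PSMA").

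**The concern.** Predictor and endpoint share a criterion (new lesions), a modality (PSMA-PET/CT) and a rule set (PERCIST). Nothing separates them in time. A castrate patient with a new soft-tissue lesion on scan 3 is PD on that scan and, on the natural reading of limb b, has CRPC on that scan.

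The primary question is whether early PSMA-PET response tells us about later CRPC. If a few patients are PD and CRPC from one image, the likelihood ratio test and the gain in c-statistic partly measure the scan predicting itself. A positive result could then arise with no true predictive value. A rule written after the data were seen would look post hoc.

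**Working it through.** **1. The texts side by side.**

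| Question | Text | Separates predictor from event? |
|---|---|---|
| Can new lesions alone give PD on scan 3? | 5.1.1, Table 1: yes | No |
| Can new lesions on PSMA-PET/CT give CRPC? | 3 and 5.1.1, limb b: yes, if castrate | No |
| Are study scans barred as endpoint evidence? | 3: barred from clinical decisions only | No |
| Must patients be CRPC-free at scan 3? | 7.1: only all three scans required | No |
| Does time start at scan 3? | 7.1: diagnosis; 3 and 5.1.1: start of ADT | No |

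The overlap has limits. PD by SUV rise alone may not meet limb b. Limb b is ambiguous about how many new bone lesions on PET suffice. Castrate testosterone is also needed.

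**2. The plan's own figure.** The plan gives no figure for this overlap. Its sample size is 150, and the Cox score-test formula is events = (1.960 + 0.842)² / [SD² × ln(HR)² × (1 − R²)].
- HR 1.2, SD 4, R² 0.75: 7.849 / (16 × 0.03324 × 0.25) = 59.0 events; divided by 0.5, N = 119.
- R² 0.80 (upper value in the Fig. 2 caption): 73.8 events, N = 148.

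The figure of 150 is thus matched at R² 0.80, not 0.75. That does not bear on this point, and N = 150 is used below.

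**3. Timing.** Scan 2 is at 2 months of ADT, upfront therapy starts before 3 months, and scan 3 follows 2 months later. Scan 3 therefore falls about 4-5 months after the start of ADT. With a 24-month median and constant hazard, the proportion with CRPC by month 4.5 is 1 − 2^(−4.5/24) = 0.122, or about 18 of 150. With a Weibull shape of 1.5 it is about 8.

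**4. Null simulation.** PET response had no true effect. Six covariates were fitted with and without PET response, and the likelihood ratio test was run at 5%.
- *From the documents:* N = 150, median 24 months from ADT, SD 40 points, R² 0.75, scan 3 at 4-5 months, follow-up 30-48 months (48-month study, 18-month accrual).
- *Assumed:* mean SUV change −40%; new lesions on scan 3 in 3%, 5% or 10% of patients; correlation of new lesions with SUV change 0 or 0.5; a fraction f of new-lesion patients counted as CRPC on the scan date. PD by SUV rise alone (about 4-6 patients) never counts as CRPC.
- *Settings:* constant hazard (1,500 runs), Weibull shape 1.5 (1,500), constant hazard with a 24-month cut-off (1,000). Ranges span settings and correlations. Monte Carlo SE is at most 1.6 points.

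Rejection with four categories:

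| f | 3% (4.5 patients) | 5% (7.5) | 10% (15) |
|---|---|---|---|
| 0 | 6-8% | 6-8% | 6-8% |
| 0.25 | 8-10% | 10-12% | 13-15% |
| 0.5 | 13-16% | 20-25% | 36-42% |
| 1 | 34-44% | 61-73% | 96-98% |

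Few patients are needed. At 5% and f = 0.5 the overlap is 150 × 0.05 × 0.5 = 3.75 patients, against about 101 events in the constant-hazard setting.

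The spurious c-statistic gain at f = 1 is 0.025-0.029, 0.035-0.040 and 0.057-0.068 for the three new-lesion rates, against 0.014-0.018 with no overlap.

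With continuous percent change, rejection is 6-7% when new lesions are unrelated to SUV change. At correlation 0.5 and f = 1 it is 6%, 9% and 12-13%.

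An independent repeat of the constant-hazard, zero-correlation case (600 runs) gave, for f = 0 / 0.25 / 0.5 / 1:
- 3% new lesions: 6 / 8 / 15 / 39%
- 5%: 7 / 11 / 22 / 64%
- 10%: 6 / 13 / 38 / 96%
- continuous coding: 5-7%

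**5. Under the proposed rule.** Rejection is 6.5-8.6% (categories) and 4.9-7.5% (continuous), the no-overlap level. A further 600-run check gave 9-10% for categories (SE about 1.2).

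**6. Power cost.** Power = Φ(√(events × SD² × (1 − R²)) × ln HR − 1.96), with HR 1.2 and SD 4.

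| Events | R² 0.75 | R² 0.80 |
|---|---|---|
| 75 (24-month cut-off, as planned) | 88% | 81% |
| 57 (24-month cut-off, proposed rule) | 79% | 69% |
| 82 (longer follow-up, proposed rule) | 91% | 84% |

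**The case against.** **Scan 3 may not be meant to trigger CRPC.** Section 3 says progression indicating CRPC leads to next-line therapy being considered at a multidisciplinary meeting. The same section keeps the extra scans out of clinical decisions, and section 8.3 says imaging will not affect therapy choice. Read together, these make high values of f less plausible. They remain rules about management, however. Section 5.2.1 has two nuclear medicine physicians read every scan for PERCIST response, so an event date could be assigned from scan 3 without any treatment decision.

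**The size is assumption-driven.** This stands. The documents give neither the new-lesion rate nor f, and results run from 8-10% (3%, f = 0.25) to near certainty. f = 1 is an upper bound. Size also depends on the model: a simpler simulation with a binary PD predictor, no other covariates and 5% PD rejected in 23% and 60% when a quarter and half of PD patients were counted.

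**The only quantified hypothesis is continuous.** Also true, and on that coding the risk is small. But the categories are what section 4.2 names as the main parameter, and section 7.1 does not settle the matter.

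**The repair costs power and touches other issues.** The power cost is real and is shown above. Excluding patients with earlier CRPC goes beyond the same-image problem, but scan 3 cannot predict events that precede it. A plain scan-3 landmark is an alternative and held rejection at 5-7% in the simpler simulation. It discards the new-lesion patients counted as CRPC, and at full overlap it left no PD patients to analyse.

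**Conclusion.** The concern holds. As written, one image can supply both the primary predictor and the primary event, and nothing in the plan prevents it. With the four PERCIST categories the false-positive rate of the primary test can rise well above 5%: 10-25% if 5% of patients have new lesions on scan 3 and a quarter to half of them are counted, and 61-73% as an upper bound if all are. Both the rate and the fraction are assumptions. With continuous percent change inflation is nil to modest (at most 12-13%). Detection bias from the unblinded scans is possible but was not quantified. Because the exposed coding is one the plan names and the primary test is affected, this should be corrected before analysis.

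**What to change.** In sections 5.1.1 and 7.1:

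1. State that, for the primary analysis, scans 2 and 3 cannot by themselves establish CRPC. The event must come from the PSA/testosterone criterion, or from imaging after scan 3 compared with scan 3.
2. Start the risk set at scan 3, among patients who have not met CRPC by other means, and list earlier events separately. Patients with new lesions on scan 3 stay in and are followed for a later event.
3. State whether the predictor is the four categories or percent change.
4. Add a sensitivity analysis using biochemical CRPC only, from the monthly PSA already collected. This also limits possible detection bias.

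These rules govern how events are counted for analysis and do not alter care.

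**Cost.** The change is wording only, with no new scans, visits or staff. About 18 of 150 patients leave the primary model under a constant hazard, or about 8 with a Weibull shape of 1.5. Events fall from about 101 to 82, from 113 to 105 (Weibull), or from 75 to 57 with a 24-month cut-off. The last case lowers power from 88% to 79% at R² 0.75, or from 81% to 69% at R² 0.80, and should be acknowledged in the sample size section. Events that scan 3 would have triggered are dated later, and time is measured from scan 3.

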5.1.2 Secondary study parameters/endpoints

- Predictive value of baseline PSMA-PET/CT imaging on time to development of CRPC.

- Predictive values of early response to ADT therapy on PSMA PET/CT (i.e. response between first and second PSMA PET/CT) according to PERCIST (PET Response Criteria In Solid Tumours).
- Predictive values of response to upfront therapy on PSMA-PET/CT (i.e. response between second and third PSMA PET/CT) according to PERCIST (PET Response Criteria In Solid Tumours).
- Analysis of response in different subgroups of patients: e.g. high versus low tumour load, high versus low PSA, high versus low Gleason score.
- -Time to initiation of second line therapy after castration-resistant disease has been found.

5.2 PSMA-PET/CT

Conform standard of care, PSMA-PET/CT will be performed before hormonal therapy is started. As part of this study, PSMA-PET/CT will be the method of imaging of first choice and repeated at standardized time-points: after 2 months (+/- 1 week) of hormonal therapy and after 2 months (+/- 1 week) of upfront therapy.

5.2.1 PSMA-PET/CT imaging protocol

PSMA-PET/CT will be performed according to standard of care, with low-dose CT using 1.5-2.0 MBq/kg of PSMA-tracer (68-Gallium PSMA and 18 Fluor PSMA are allowed). Image reconstruction will be performed according to EARL accreditation.(Boellaard 2015) The used PSMA tracer may vary between participating centers, but in each center the same tracer will be used at baseline and during follow-up. Image acquisition starts 60 minutes (+/- 15 minutes is acceptable) after injection from head to upper thigh. Effective absorbed dose is approximately 6 mSv, which is similar to a full-dose CT scan of the abdomen. IV drip is necessary to inject the tracer.

The scans will be examine by the local nuclear medicine physician and afterwards two experienced nuclear medicine physicians will examine all PSMA-PET/CT images. The following parameters will be assessed:

- TNM stage.
- Response according to PERCIST (in follow-up scans).
- PiP-RADS scores.
- Location and number of prostate lesions, lymph node metastases and distant metastases.
- Activity (SUVIbm-mean, SUVIbm-peak, SUVIbm-max) of all lesions.

5.2.1.1 Timing first PSMA-PET/CT – baseline First PSMA-PET/CT needs to be performed <4 weeks before start ADT.

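### The uptake-time window applies to each scan, so one man's scans 2 and 3 may differ by up to 30 minutes; matching them would be a cheap gain in precision.

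*Combined protocol and SAP*

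**What the plan says.** Section 5.2.1 gives one acquisition window for all scans: "Image acquisition starts 60 minutes (+/- 15 minutes is acceptable) after injection from head to upper thigh". The only consistency rule there concerns the tracer: "in each center the same tracer will be used at baseline and during follow-up". EARL is cited for image reconstruction, and uptake time is not among the parameters listed for assessment. Sections 5.2, 5.2.1.2 and 5.2.1.3 fix the calendar timing of scans 2 and 3 to within a week. They do not address the interval from injection to acquisition.

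Section 5.1.1 describes PERCIST as follows: "It divides tumor response based on the perceptual change in SUV between two (in our case) PSMA PET/CT's". In its Table 1, partial response needs "More than or equal to 30% reduction of SUV" and progression "More than or equal to 30% increase in SUV", each with an absolute change of 0.8 SUV units. Progression can also be called on new lesions. The interval to be noted with a PERCIST result is the time between the two scans, not the uptake time.

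The upfront-therapy response is the "response between second and third PSMA PET/CT" (section 5.1.2; section 2 makes it the primary predictor). The Cox models in section 7.1 adjust for six factors, ending with "type of upfront therapy, PSMA response to hormonal therapy only". Uptake time is not one of them, and no sensitivity analysis on it is planned.

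**The concern.** In a paired measurement, the difference in uptake time between the two scans enters the result. A per-scan window of 45 to 75 minutes limits that difference only to 30 minutes. If lesion SUV changes over that part of the uptake curve, some of the measured response reflects scanner timing.

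Two consequences could follow, one for each form in which the plan uses the predictor. As a continuous percentage change (the form behind the sample size inputs in section 4.2), added noise attenuates the hazard ratio and the gain in c-statistic. The likelihood ratio test uses only the part of the predictor that the other six factors do not explain, so the noise has to be judged against that smaller residual spread. In the CR/PR/SD/PD form, men near the 30% limits can be put in the wrong category.

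**Working it through.** **Inputs from the sample size section (4.2):** SD of PSMA response 3.5 to 4 units of 10 percentage points; R² 0.75 (0.75-0.80 in the Figure 2 caption); hazard ratio 1.2-1.3 per 10 points; event probability 0.5; N = 150, so 75 events; power 80%; "Type I error (alpha) 5%, two-sided".

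**The plan's own figure.** Events = (1.96 + 0.84)² / [SD² × (1 − R²) × (ln HR)²], and N = events / 0.5.
- SD 4, R² 0.75, HR 1.2: 59.0 events, N = 119. With HR 1.3, N = 58. The stated 150 is not reproduced from the R² in that sentence.
- SD 4, R² 0.80, HR 1.2: 73.8 events, N = 148, which agrees with 150.

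That mismatch is a separate matter. I use R² 0.75 as the base and show R² 0.80 as well.

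**Assumptions not in the documents.** Lesion SUV drifts linearly by 0.25-1.0% of its 60-minute value per minute. Uptake times are independent and uniform over 45-75 minutes. The man has no true SUV change. The planning SD contains no timing noise.

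**Step 1: the largest gap.** 75 − 45 = 30 minutes, or about 30 × 0.25 = 7.5 to 30 × 1.0 = 30 points. As an exact ratio at 1.0% per minute, 1.15/0.85 = 1.353 (+35%) and 0.85/1.15 = 0.739 (−26%). With no true change, timing alone reaches +30% only at about 0.87% per minute or more, and −30% only at about 1.18%, which is beyond the assumed range.

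**Step 2: typical noise.** SD of the gap = 15 × √(2/3) = 12.25 minutes; 44% of pairs differ by more than 10 minutes. Noise SD = 12.25 × drift. Residual SD of the predictor = 40 × √0.25 = 20 points. Reliability = 400 / (400 + noise²). Power = Φ(√(75 × 16 × 0.25 × reliability) × ln 1.2 − 1.96), and attenuated HR = exp(reliability × ln 1.2).

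| Drift per minute | Noise SD (points) | Reliability | HR seen | Power |
|---|---|---|---|---|
| none | 0 | 1 | 1.20 | 88.5% |
| 0.25% | 3.1 | 0.98 | 1.20 | 88% |
| 0.5% | 6.1 | 0.91 | 1.18 | 85.5% |
| 1.0% | 12.2 | 0.73 | 1.14 | 77% |

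**Step 3: relaxing the worst case, at 1.0% per minute.**
- Times clustered at 60 minutes (assumed SD 5): gap SD 5 × √2 = 7.1 minutes, reliability 400/450 = 0.89, power about 85%.
- True 50% SUV fall: noise halves to 6.1 points, power 85.5%.
- HR 1.3: power goes from 99.5% to 97%.

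**Step 4: R² 0.80.** Residual variance is 1600 × 0.20 = 320. Power starts at 80.6% and, under the same worst-case assumptions, is about 76% at 0.5% per minute and 64% at 1.0%.

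**Step 5: men near a limit.** At 0.5% per minute with uniform times, simulation gives a true 25% fall read as at least 30% in 15% of pairs, and a true 32% fall missed in about 32%. This looks at the percentage limit only, not the 0.8-unit condition.

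**Step 6: with matching.** Scan 3 held directly within 5 minutes of scan 2 gives a gap SD of 2.8 minutes and, at 1.0% per minute and R² 0.75, power of 88%. Within 10 minutes, the gap SD is 5.3 minutes and power 86%.

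**The case against.** The strongest reply is that every harm figure depends on a drift rate that the documents do not contain, combined with unfavourable choices. Sixty minutes is the target and 15 either way only the tolerance, so uniform times are pessimistic. The error scales with the true SUV ratio, so it shrinks in men who respond. The planning SD was estimated from a case series of measured responses and may already contain timing noise, in which case adding it again counts it twice. The PERCIST and imaging guidance cited may carry a pairing rule, which cannot be checked here. Complete response and progression by new lesions do not depend on the percentage limits. Finally, a marker meant for routine use will meet ordinary timing variation anyway.

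Most of this stands, and it limits the size of the point. It does not remove it: the protocol itself restates no matching rule, does not list uptake time for recording, and has no analysis that would show whether timing mattered.

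A reader might infer that the study is measuring acquisition timing instead of response, or that timing could create a false association with castration resistance. The documents support neither. Timing would be one component of the measured change, of unknown size, and a false association would require uptake time to be related to outcome, which nothing in the plan suggests.

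**Conclusion.** The point holds as a cheap improvement in precision, not as a flaw that threatens the primary analysis. The text is clear: a 30-minute difference within the primary scan pair is in protocol, and section 7.1 does not deal with it. The consequence is conditional on SUV drifting with uptake time. In the worst case described, power at R² 0.75 and hazard ratio 1.2 falls from 88.5% to 88-77%, and only the steep end of the assumed range goes below the planned 80%. At R² 0.80 there is almost no margin to begin with, so the same noise would take power below 80% across the range. A reader might conclude from this that the study is underpowered because of timing. That does not follow without a known drift rate and the other worst-case assumptions.

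One feature is not in these figures. Scan 2 ends the hormonal-therapy response and starts the upfront response, so its timing error enters two covariates of the same model with opposite sign.

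**What to change.** In section 5.2.1:
- Keep 60 ± 15 minutes as the outer limit for every scan.
- Record injection time and acquisition start time for all three scans.
- Aim to start scan 3 within ± 5 minutes (at most ± 10) of the same patient's scan 2 uptake time, and scan 2 likewise relative to scan 1 where the scan 1 time is known.

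Scan 3 should be tied directly to scan 2. If both were tied only to scan 1, the primary pair could still differ by 10 minutes under a ± 5 rule and by 20 under ± 10. Scan 1 is also a standard-of-care scan usually done before inclusion (section 5.7), so its uptake time may not be available.

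In section 7.1, pre-specify a sensitivity analysis that either adjusts for the scan 2-3 uptake-time difference or excludes pairs more than 10 minutes apart.

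The cost is two recorded times per scan, one extra analysis and somewhat less slack on the scanner list. No procedure, radiation exposure or patient is added. The recorded times would be useful even if drift proves negligible, because timing cannot reliably be adjusted for later if it was not recorded.
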